1.3 SCHEDULE OF ACTIVITIES

Table 1. Schedule of Activities

	Study Visit (window, in days)								
Procedure/Evaluation	V ₁ D0	V ₁ D7 (± 1)	V ₁ D14 (± 2)	V ₂ D0 (± 2)	V ₂ D7 (± 2)	V ₂ D14 (± 2)	V ₂ D28 (± 7)	V ₂ D56 (± 7)	V ₂ D182 (± 7)
Written informed consent	Xa								
Randomization	Xa								
Medical/Medication history	Xa	X	X	Xa	X	X	X	X	X
Clinician assessment and PE	Xa	X	X	Xa	X	X	X	X	X
Vaccine injection-site and AE assessment		X	X	Xa	X	X			
Survey distribution ^b	X			X					
Survey review		X			X				
Vital signs ^c	Xa	X	X	Xa	X	X	X	X	X
Urine pregnancy test ^d	Xa			Xa					
Urine drug test	Xa								
Nasal SAM	Xa	X	X	Xa	X	X	X	X	X
Nasal cytology brushing		Xe			Xe				
Vaccination	Xf			Xf					
CBC + diff	Xa	X	X	Xa	X	X	X	X	X
Acute care, mineral, and hepatic panels	Xª	X	X	Xª	X	X	X	X	X
LDH, uric acid, creatine kinase, and total protein	Xª	X	X	Xa	X	X	X	X	X
HLA testing	Xa								
Serum collection	Xa	X	X	Xa	X	X	X	X	X
Whole blood collection (PBMC)	Xa	X	X	Xa	X	X	X	X	X
Whole blood collection (PAXgene)	Xa	X		Xa	X				

AE = adverse event; CBC + diff = complete blood count with differential; D = day; HLA = human leukocyte antigen; LDH = lactate dehydrogenase; PBMC = peripheral blood mononuclear cells; PE = physical exam; SAM = synthetic absorptive matrices; X = to be performed.

Notes:

[•] Screening will be performed under NIH screening protocol 11-I-0183.

- If medically necessary (e.g., if a safety condition arises), the participant may be asked to return for an unscheduled interim visit for AE assessment and other safety assessments as appropriate.
- Acute care panel includes Sodium (NA), Potassium (K), Chloride (CL) Total CO2 (Bicarbonate), Creatinine, Glucose, Urea nitrogen, eGFR, Anion Gap
- Mineral panel includes Albumin, Calcium, Magnesium (Mg), and Phosphorus.
- Hepatic panel includes Alkaline Phosphatase, ALT/GPT, AST/GOT, Total Bilirubin, Direct Bilirubin
- ^a Complete prior to vaccine administration.
- ^b Survey (paper or electronic) will be completed each evening for 7 evenings starting V₁D0 and for another 7 evenings starting V₂D0 to capture temperature and any local symptoms (e.g. redness, swelling, and pain) or general symptoms (e.g., fever, chills, headache, myalgia, arthralgia, fatigue, nausea, vomiting).

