In ferrets, broad, potent, protective efficacy was observed against mismatched and completely heterosubtypic challenge with a variety of influenza virus challenge strains. Vaccinated ferrets showed marked abrogation of pneumonia as assessed by histopathology (Figure 5) and immunohistochemistry (Figure 6) for viral antigen as well as reduced viral loads (Figure 6). Lung sections of unvaccinated ferrets showed marked pathological changes involving over 50% of the lung parenchyma, including multifocal, moderate-to-severe, necrotizing bronchitis and bronchiolitis, along with moderate-to-severe alveolitis with a mixed inflammatory cell infiltrate, and focal pulmonary edema and fibrinous exudates. In a separate experiment (data not shown) with ferrets to determine the effect of pre-existing immunity on vaccine response, animals were exposed to either seasonal H1N1 and H3N2 viruses prior to vaccination. Subsequent vaccine-associated protective efficacy was still demonstrated after challenge with heterosubtypic virus (H3N2 for animals initially exposed to H1N1, and H1N1 for animals initially exposed to H3N2). These data suggest that protective efficacy is not negatively impacted by pre-existing immunity from prior influenza virus exposure.

[figure not shown]

Figure 3a,b,c. Serum IgG and BAL IgA titers against HA (H1, H3, H5, H7) and NA (N1, N3, N8, N9) as measured by ELISA area-under-the-curve (AUC) in mice vaccinated with intramuscular (IM) BPL-1357, intranasal (IN) BPL-1357, or mock vaccine.

^{*} denotes p<0.05. ** denotes p<0.01. *** denotes p<0.001.

[figure not shown]

Figure 3d,e,f. Serum IgG and BAL IgA titers against HA (H1, H3, H5, H7) and NA (N1, N3, N8, N9) as measured by ELISA area-under-the-curve (AUC) in mice vaccinated with intramuscular (IM) BPL-1357, intranasal (IN) BPL-1357, or mock vaccine. Serum hemagglutinin inhibiting antibody titers also provided.

^{*} denotes p<0.05. ** denotes p<0.01. *** denotes p<0.001.

[figure not shown]

Figure 4. Weight loss and survival following lethal challenge with H1N1 (A), H5N1 (B), H5N8 (C), H6N1 (D), H7N1 (E), H7N9 (F), and H10N7 (G) in mice vaccinated with intramuscular (IM) BPL-1357, intranasal (IN) BPL-1357, or mock vaccine. DPC=days post challenge.

[figure not shown]

Figure 5. Ferret histopathology following viral challenge in ferrets vaccinated with BPL-1357 intramuscularly (IM), intranasally (IN), or mock vaccine.

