9.2 SAMPLE SIZE DETERMINATION

There will be 15 participants in each treatment group. The study will have adequate power to observe safety signals as defined by the 2 pausing criteria.

 A subject experiences an SAE that is unexpected (per the investigator's brochure or product label) and possibly, probably, or definitely related to a study agent or route of administration;

• A subject experiences two grade 3 or greater AEs that are unexpected (per the investigator's brochure or product label) and possibly, probably, or definitely related to a study agent or route of administration.

Table 7 gives the probability of meeting either criteria in just one arm under various true rates. The table shows that if the true rate in a single vaccine arm is 15% there would be a high probability of detecting the safety signal (power of 0.913). If we meet pausing criteria in both arms, then we also meet halting criteria for study.

Table 8. Probability of meeting pausing criteria

True rate of pausing	Probability of pausing
criteria 1 or 2 (%)	(≥ 1/15)
5%	0.537
10%	0.794
15%	0.913

We will also compare AE rates for the combined vaccine arms to the placebo arm at V_2D28 . We will use a 1-sided .05 level test for the comparison of proportions. With this test we will have 80% power if the true rate in the placebo arm is 5% and the true rate in the vaccine arms is 36%. We will also have 80% power if the true rate in the placebo arm is 10% and the true rate in the vaccine arms is 44%. (This calculation was performed using the SWOG statistical tool website with no continuity correction).

For the safety secondary objective we will compares AE rates in a similar manner but at the end of study, V_2D182 . For the immunogenicity secondary objective, we will compare antibodies against H1, H3, H5, H7, N1, N3, N8, and N9 from both blood and mucosal samples between all 3 arms at V_2D28 . With 15 participants in each arm there will be power of 0.82 to detect an effective size of 1.25 (the effective size is the mean/std) using a two-sided 0.05/3=.0167 level t-test. The level of the test has been adjusted to control for the 3 comparisons between all groups. A similar analysis will be performed at other timepoints for one of the exploratory objectives.

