9.4 STATISTICAL ANALYSES

9.4.1 General Approach

AE's and SAE's will be tabulated by severity and by group. Tests of proportions with no continuity correction will be used to test for differences between groups. Confidence intervals around the difference in proportions will be calculated. Antibodies will be compared using t-tests. Antibody data may be transformed by using log transformation to stabilize the variance if the data are skewed.

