9.4.2 Analysis of the Primary Endpoints

If 1 or more related SAE's are observed in an arm, the primary safety endpoint for that arm will have been met. For the AE safety endpoints, summary statistics will be provided for unexpected safety events. Unexpected safety events will be summarized by treatment group, as well as by individual AE and grouped by type of event. Tests of proportions will be used to compare rates between groups. 90% confidence intervals will be calculated for safety endpoints. This will be done at V_2D28 for the primary endpoint, but a similar analysis will be done for the secondary safety endpoint at V_2D182 .

Two-sided t-tests will be used to compare antibody endpoints at V_2D28 for the secondary objective. All three arms will be compared to each other. A 0.05/3=0.0167 significance level will be used to adjust for the 3 group comparisons. Confidence intervals around group differences will be calculated using the significance level adjusting for the 3 comparisons (each confidence interval will be at the 1-0.0167=0.983 level). Antibody data maybe transformed by using the log10 transformation to stabilize the variance if the data are skewed.

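### The secondary V2D28 antibody comparison is an unadjusted t-test on a scale fixed only after seeing the data, although pre-vaccination serum and nasal samples are taken from every participant

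*Combined protocol and SAP*

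**What the plan says.** For the secondary immunogenicity objective, section 9.4.1 says "Antibodies will be compared using t-tests", and section 9.4.2 repeats this for the V2D28 endpoints: "Two-sided t-tests will be used to compare antibody endpoints at" V2D28. All three pairs of arms are compared: "A 0.05/3=0.0167 significance level will be used to adjust for the 3 group comparisons". Intervals are at the matching 98.3% level. Section 9.2 gives power of 0.82 for a standardised effect of 1.25 with 15 per arm.

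On scale, section 9.4.1 says "Antibody data may be transformed by using log transformation to stabilize the variance if the data are skewed", and section 9.4.2 says "Antibody data maybe transformed by using the log10 transformation to stabilize the variance if the data are skewed". Neither gives a criterion for skewness.

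On baseline:
- Table 1 (section 1.3) schedules serum and nasal SAM at V1D0 with the footnote "Complete prior to vaccine administration", so both compartments are sampled before the first dose.
- V1D0 is not a listed antibody timepoint. The secondary endpoint is at V2D28, and the tertiary endpoints run from V1D7 to V2D182.
- Baseline antibody level is not among the characteristics named in section 9.4.3, and section 6.3.1 names no stratification factor.
- Covariate regression and GEE appear only in section 9.4.6, as optional exploratory methods with no covariate named.

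**The concern.** Participants are adults up to 55, and section 5.1 bars influenza vaccination only in the 8 weeks before enrolment. For some of the measured antibodies, people will differ before dosing, and part of that difference may still be present at V2D28. The planned test treats all of it as noise. With 15 per arm this could matter to whether a real difference between routes, or between vaccine and placebo, is detected, and to the width of the reported intervals.

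The scale is a second, smaller issue. On the original scale the comparison estimates a difference in mean titre; on the log scale it estimates a ratio of geometric means. Because the choice follows inspection of the data, without a stated rule, the estimated quantity is not fixed in advance and could differ from one antigen or compartment to the next.

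**Working it through.** **Inputs.** From sections 9.2 and 9.4.2: n = 15 per arm ("There will be 15 participants in each treatment group"), effect d = 1.25 SD, two-sided alpha = 0.05/3 = 0.0167. Assumed, because the documents do not give it: the correlation r between the V1D0 and V2D28 values, shown from 0 to 0.7.

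**1. The plan's own figure.** The noncentrality is d × √(n/2) = 1.25 × √7.5 = 3.423.
- Two arms only, 28 df, critical t = 2.546: power 0.803.
- Variance pooled over three arms, 42 df, critical t = 2.494: power 0.819.

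The stated 0.82 therefore reproduces as an unadjusted t-test and uses no baseline information.

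**2. Three-arm ANCOVA on the V1D0 value.** Residual variance is multiplied by (1 − r²). Estimating the slope costs, on average, a factor 1 + 1/(42 − 2) = 1.025. One degree of freedom is lost (41 df, critical t = 2.496). The noncentrality is 3.423 / √[(1 − r²) × 1.025].

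| r (assumed) | Noncentrality | Power, formula | Power, simulation (40,000 runs) |
|---|---|---|---|
| 0 | 3.381 | 0.807 | 0.811 |
| 0.3 | 3.545 | 0.847 | 0.849 |
| 0.5 | 3.904 | 0.915 | 0.913 |
| 0.7 | 4.735 | 0.985 | 0.985 |

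The like-for-like comparator is 0.819 (0.82 in simulation).

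**3. Break-even.** The formula gives 0.817 at r = 0.15 and 0.825 at r = 0.2, so the three-arm model breaks even between these. With two arms only, ANCOVA has 0.784 at r = 0 and 0.802 at r = 0.2 against 0.803, so it breaks even at about 0.2.

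**4. Equivalent sample size.** In large samples, adjustment is worth 15/(1 − r²) per arm: 16.5, 20.0 and 29.4 at r = 0.3, 0.5 and 0.7.

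**5. Where the noise comes from.** The difference in mean baseline between two arms has standard error √(2/15) = 0.365 SD and exceeds 0.5 SD in 17% of trials. An imbalance of 0.5 SD moves the unadjusted V2D28 difference by 0.5r: 0.15, 0.25 and 0.35 SD at r = 0.3, 0.5 and 0.7. This is the same loss as in step 2 seen in a single trial, not a further one.

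**6. Validity.** Under no effect, both tests rejected in 0.016 to 0.018 of simulated trials, against a nominal 0.0167.

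**The case against.** The strongest reply is that this is a matter of efficiency and not an error. The t-test holds its level, the stated power is right, and immunogenicity is secondary in a phase 1 safety trial. All of that stands.

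The second reply is that the gain rests on an undocumented correlation. That also stands. Section 2.2 names H1N1 and H3N2 as the annual epidemic strains. Five of the eight antigens (H5, H7, N3, N8, N9) belong to neither, so baseline values there may sit near the detection limit and predict little. The documents say nothing about how repeatable nasal SAM titres are. The gain may be nil for such endpoints, with a loss of up to 1 to 2 points.

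Several stronger inferences are tempting but unsupported:
- *Chance imbalance biases the test.* Randomisation protects the type I error, and the imbalance is already in the t-test's standard error. It can only move the one observed estimate.
- *The analysis uses untransformed titres.* Log transformation is expressly allowed; what is missing is a commitment made in advance.
- *Baseline titres are already in hand.* The specimens are collected, but no listed endpoint includes a V1D0 antibody result.
- *This is the trial's only formal immunogenicity test.* Sections 9.2 and 9.4.6 also plan tests at other timepoints and for exploratory endpoints.
- *The ferret experiment on prior exposure shows that baseline matters here.* It concerns protection after challenge in ferrets and says nothing about how well a human V1D0 titre predicts the V2D28 titre.

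**Conclusion.** The point holds as an avoidable loss of precision and an open choice of scale, not as an invalid analysis. Against 0.82 for the pooled t-test, adjustment gives about 0.81, 0.85, 0.91 and 0.985 at assumed correlations of 0, 0.3, 0.5 and 0.7: roughly 1 point lost at zero, 3 gained at 0.3, and 9 to 10 gained at 0.5. These figures assume 15 evaluable per arm, normal residuals with equal variance on the analysis scale, and a common slope across arms. The exchange favours adjustment if the correlation exceeds about 0.2. That is plausible for the H1, H3 and N1 endpoints and uncertain for the others. The change is worth making before unblinding, but the trial does not fail without it.

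**What to change.** In sections 9.2, 9.4.1 and 9.4.2:
1. Specify that antibody is assayed on the V1D0 serum and nasal SAM, for each antigen, assay and compartment to be compared at V2D28.
2. Fix the log10 scale in advance and remove the condition on skewness.
3. Replace the pairwise t-tests with one linear model per antigen, assay and compartment, fitted to all three arms: log10 V2D28 titre on treatment group and log10 V1D0 titre. Keep 0.0167 per pairwise comparison and the 98.3% intervals. Report baseline-adjusted geometric mean ratios.
4. In section 9.2, keep 0.82 at 1.25 SD as the unadjusted reference, and state that the gain from adjustment depends on a correlation not yet known.

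The cost is wording, laboratory work on V1D0 samples that are already collected, one degree of freedom, and about 1 to 2 points of power for any endpoint where baseline proves uninformative. No new visit or sample is needed.

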4 STUDY DESIGN

4.1 OVERALL DESIGN

This is a randomized, placebo-controlled, single-center, phase 1 clinical trial of BPL-1357 administered via IM or IN routes. The primary safety hypothesis is that BPL-1357 given IN or IM will be well-tolerated with minor side effects.

Participants will be randomized 1:1:1 to one of three groups:

- Group A will receive IM BPL-1357 plus IN placebo.
- Group B will receive IM placebo plus IN BPL-1357.
- Group C will receive IM and IN placebo.

This study will test a single dose of vaccine given at two timepoints 28 days apart. Group C will receive IM and IN placebo.

For each participant, the duration of study participation will be about 7 months (Figure 2). Participants will be followed regularly for 210 days to assess for side effects and to collect nasal mucosal and blood samples to evaluate immunity and characterize immune response. Participants will receive the intervention on 'vaccine 1 day 0' (V₁D0) and will return for followup on vaccine 1 day 7±1 14±2, and 28±2. They will receive the second dose of vaccine/placebo on 'day 28', referred to as 'vaccine 2 day 0' (V₂D0). Subsequent visits will be scheduled with respect to the timing of V₂D0 (i.e. V₂D7 will be scheduled for 7 days after V₂D0 and not 35 days after V₁D0, if there is disagreement between the two). Participants will return for follow-up on vaccine 2 day 7±2, 14±2, 28±7, 56±7, and 182±7 (Table 1). Participants will also complete a survey questionnaire at home for 7 days after each vaccine dose to further evaluate safety (APPENDIX A). Participants will be sent home with a thermometer to facilitate at home temperature monitoring and instructions will be provided (APPENDIX B). Participants who develop symptoms concerning for influenza-like illness (ILI) (including but not limited to rhinorrhea, sore throat, change in smell or taste, cough, wheezing, dyspnea, fatigue, weakness, malaise, dizziness, fever, chills, headache, myalgias, arthralgias, diarrhea) will contact the study team regarding evaluation. Those with confirmed influenza-like illness by the study team who are unable to be evaluated expeditiously at NIH will be instructed to perform an at-home nasal swab and/or nasal SAM and send the specimens in for testing. Collection and packing materials will be provided to participants either in person or will be mailed to participants. Detailed instructions for sample collection and packaging will be given to participants (APPENDIX C).

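### Bonferroni at 0.05/3 for the three antibody comparisons is valid, but Holm or a closed test would give more power at 15 per arm; separately, the 16 to 24 antibody endpoints carry no error control or test count

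*Combined protocol and SAP*

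**What the plan says.** Section 9.2 sets out the secondary immunogenicity comparison at V2D28: "we will compare antibodies against H1, H3, H5, H7, N1, N3, N8, and N9 from both blood and mucosal samples between all 3 arms". The test is a "two-sided 0.05/3=.0167 level t-test", and the reason given is that "The level of the test has been adjusted to control for the 3 comparisons between all groups". Section 9.4.2 repeats the rule ("A 0.05/3=0.0167 significance level will be used to adjust for the 3 group comparisons") and uses the same level for the intervals, so each pairwise difference gets a 98.3% confidence interval.

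The power statement in section 9.2 is: "With 15 participants in each arm there will be power of 0.82 to detect an effective size of 1.25", where "the effective size is the mean/std".

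The endpoint lists in section 1.1 and Table 2 name head and stalk antibodies for the four HA subtypes, plus four NA subtypes, in blood and in mucosal samples. The plan does not name a key antibody endpoint, adjust across antigens or compartments, or label these results descriptive. Section 9.4.6 asks for a discussion of how many endpoints were analysed, but only for the exploratory analyses.

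**The concern.** There are two separate issues.

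**Efficiency within an endpoint.** With exactly three arms, if any two of the pairwise null hypotheses are true, all three are. A global test at 0.05 followed by pairwise tests at 0.05 therefore controls the family-wise error strongly at 5%. Holm gives the same guarantee and rejects everything that plain Bonferroni rejects. At a fixed 15 per arm, plain Bonferroni leaves some power unused.

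**Multiplicity across endpoints.** The plan adjusts for the smaller multiplicity (three contrasts) and says nothing on the larger one (16 to 24 endpoints, hence 48 to 72 contrasts). A reader of the results could not tell how many antigen-level differences to expect by chance.

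**Working it through.** **Inputs.** From section 9.2: n = 15 per arm ("There will be 15 participants in each treatment group"), effect 1.25, two-sided level 0.05/3 = 0.0167. From section 4.1: 1:1:1 allocation. The effect is read as a mean difference in SD units, so SD = 1. No dropout is allowed for.

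**1. The plan's own power.** Noncentral t with ncp = 1.25 × √(15/2) = 3.42:
- 28 df (two-sample t-test): power 0.803
- 42 df (SD pooled over three arms): power 0.819

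The stated 0.82 is reproduced.

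**2. Alternatives with the same 5% guarantee.** Simulated normal data, 15 per arm, 100,000 trials per scenario, Welch tests. The closed procedure is Welch ANOVA at 0.05, then each Welch t-test at 0.05.

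| Both vaccine arms 1.25 SD above placebo | Bonferroni | Holm | Closed |
|---|---|---|---|
| Power, each vaccine-placebo contrast | 0.80 | 0.83 | 0.88 |
| Power, both routes beat placebo | 0.69 | 0.75 | 0.84 |

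With one arm midway (0, 0.625, 1.25), the 1.25 SD contrast goes from 0.80 to 0.83 under the closed procedure, and each 0.625 SD contrast from 0.22 to 0.37. With arms spaced 1.25 SD apart (Student t, 400,000 trials), adjacent contrasts go from 0.80 to 0.91. The gain on a 1.25 SD contrast therefore runs from about 3 to 11 points, depending on the third arm.

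**3. Error within one endpoint.**
- Global null, family-wise error: about 0.044 for Bonferroni, 0.049 to 0.050 for closed.
- One equal pair, the other arm 1.25 SD away: 0.016 to 0.017 for Bonferroni, 0.039 for Holm, 0.049 to 0.050 for closed.
- Closed error also stays within 5% with placebo SD 0.2 against 1 in the vaccine arms.

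**4. Number of endpoints.** Low count: 8 antigens × 2 compartments = 16. High count: (4 heads + 4 stalks + 4 NA) × 2 = 24. Contrasts: 16 × 3 = 48 and 24 × 3 = 72. Both counts take one assay per antigen.

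**5. Error across endpoints under the plan's tests, global null.** With independent endpoints and 0.044 per endpoint, 1 − (1 − 0.044)^16 ≈ 0.51 and 1 − (1 − 0.044)^24 ≈ 0.66. Direct simulation (20,000 trials each) gives:

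| Assumed correlation | 16 endpoints | 24 endpoints |
|---|---|---|
| 0 | 0.52 | 0.66 |
| 0.5 | 0.36 | 0.45 |
| 0.8 | 0.21 | 0.24 |

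The documents give no correlations, so the last two rows are assumptions.

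**6. Bonferroni over everything.** At 0.05/48 or 0.05/72, power for a 1.25 SD contrast falls to 0.43 or 0.38. That is a poor remedy at this sample size.

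**The case against.** The plan pre-specifies a valid adjustment, states it the same way in two sections, and meets its own power claim. Antibodies are a secondary objective in a phase 1 trial whose sample size is argued first from the pausing criteria. All of this stands, so the choice of Bonferroni is not an error.

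A reader might infer that Bonferroni costs power for no extra protection. The documents do not support that. Section 9.4.2 builds its 98.3% intervals at the same level, so test and simultaneous interval agree, and realised error is lower when one pair is equal (about 0.016). Holm and the closed test give up both. Every pairwise rejection they add has p between 0.0167 and 0.05, so its 98.3% interval covers zero. This describes the entire gain, not just borderline cases.

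It is also fair that a looser threshold adds to the problem across endpoints. Suppose IM and IN are equal and both beat placebo. The chance of at least one false IM-IN claim over 16 independent endpoints is 1 − (1 − 0.0167)^16 = 0.24 under the plan, and up to 1 − 0.95^16 = 0.56 under the closed test. For 24 endpoints the figures are 0.33 and 0.71. The change therefore should not be made without q-values and a test count.

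Finally, the headline scenario has both routes doing equally well in the same compartment. Section 2.2 reports that in mice IM gave stronger serum titers and IN stronger mucosal titers. The gain on the larger contrast may then be nearer 3 points, although the smaller contrasts, including IM against IN, gain more.

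**Conclusion.** This is a worthwhile, low-cost improvement, not a correction of a mistake. With both vaccine arms 1.25 SD above placebo, Holm adds about 3 points of power per contrast and the closed Welch procedure about 8. For showing that both routes beat placebo, the gains are about 6 and 15 points (0.69 to 0.75 and 0.84). A fixed loss of 8 points should not be inferred, because the gain depends on where the third arm lies. These figures assume normal data after any log transformation and 15 evaluable participants per arm.

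The gap across endpoints is the stronger half. No section controls error over the 16 to 24 endpoints or asks for their number to be reported with the results. The endpoints are listed in advance, so a reader should not infer that they are hidden. Nor should 0.56 and 0.71 be quoted as the plan's error across endpoints under the global null, since they assume exactly 5% per endpoint. The plan's own tests give about 0.52 and 0.66 if endpoints are independent, and less if they are correlated.

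**What to change.** In sections 9.2 and 9.4.2:
1. Replace plain Bonferroni with Holm at minimum, or with Welch ANOVA at 0.05 followed by Welch t-tests at 0.05. Name one procedure before unblinding, which section 6.3.3 places after the last V2D182 visit. Holm keeps every Bonferroni rejection; the closed version is usually more powerful but can occasionally lose one when the global test fails.
2. Keep the 98.3% intervals and label them simultaneous intervals.
3. Report Benjamini-Hochberg q-values across all antigen-by-compartment contrasts beside the arm-adjusted p-values, with the number tested, and extend the section 9.4.6 disclosure to this objective.
4. State the downside: every added pairwise rejection has a 98.3% interval that includes zero, and realised error when one pair is equal rises from about 0.016 to as much as 0.05.

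The cost is a few lines of text and one extra table column. No further participants are needed. If the sponsor prefers to keep Bonferroni for its match with the intervals, item 3 is still needed.
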